8.1 General Conventions

Data will be summarized in tables and further details at a granular-level data will be provided in listings.

Descriptive statistical analyses will be provided for pre-specified study endpoints. Summaries for continuous variables will include number of observations (n), mean, standard deviation, median, minimum, and maximum. Summaries for categorical variables will include total and counts for each category and their corresponding percentages.

Data recorded at the nominal visits or unscheduled visits will be presented in summary tables; however, data captured at unscheduled visits will not be included

in “by visit” summary tables. Listings will include data for both scheduled and unscheduled visits.

Analyses will be conducted using SAS version 9.4 or higher. During the course of statistical programming of tables that are mocked up in this SAP, minor modifications may become necessary. Examples of these minor modifications include, but are not limited to, re-wording of a footnote, addition of a footnote, re-labeling of a column, or addition or removal of a column from a table or listing. In cases where modifications to tables or listings are not related to a change in statistical analysis methodology or conclusions that could be made on the originally proposed methodology, no amendment of the SAP will be necessary. Any final analyses that differ from what has been specified in this document will be identified within the final statistical output and documented within the clinical study report.

8.2 Disposition of Study Subjects

Subject disposition will be summarized using counts and percentages. The number and percentage of subjects screened, enrolled, completed, and discontinued will be tabulated along with the specific reasons for discontinuation (CRF page Subject Completion/Discontinuation).

8.3 Demographic and Baseline Characteristics

Summary statistics will be provided for subject demographics (age, childbearing potential, race, and ethnicity), vital signs that include height, weight, and BMI, and smoking history. Listings will be presented for subject’s inclusion/exclusion criteria, demographic and baseline characteristics.

Medical history will be summarized by Medical Dictionary for Regulatory Activities (MedDRA) system organ class and preferred term. A listing will be presented for medical history. Surgical history, treatment history, and concomitant medications will be listed only.

8.4 Endpoint(s) and Associated Hypotheses

There will be no hypothesis testing conducted for the primary or secondary endpoints. Two-sided 95% CIs will be estimated for selected endpoints for descriptive purposes.

8.4.1 Primary Endpoint

Perioperative endpoint-

1. Technical success, defined as ablation of the target lesion(s) according to the protocol and covered completely, with an adequate margin, as defined by the performing physician (i.e., the ablation zone completely overlaps or

encompasses the target lesion(s) plus an ablative margin), as assessed by CT, MRI, PET, US, and/or X-ray, immediately following the procedure. Technical Success is assessed at Visit 2 following the ablation of the target lesion.

Short term endpoint -

2. Technique efficacy, ablation of the target lesion(s) according to the protocol and covered completely, with an adequate margin, as defined by the performing physician (i.e., the ablation zone completely overlaps or encompasses the target lesion(s) plus an ablative margin), as assessed by CT, MRI, PET, US, and/or X-ray, at Visit 3 (between 7 days and less than 3 months post-ablation).

Long term endpoint -

3. Target lesion recurrence (local recurrence) rate evaluated at every visit starting from visit 4 after the primary ablation at visit 2 of the target lesion(s), and overall evaluation at the 5-year follow-up, as assessed by CT, MRI, PET, US, and/or X-ray.

8.4.2 Secondary Endpoints

Secondary endpoints of this registry are:

1. Secondary efficacy rate, defined as the percentage of soft tissue lesions that have undergone successful repeat ablations (target or non-target) following identification of local soft tissue lesion progression. A successful repeat ablation will be defined as ablation of the lesion according to the protocol and covered completely, with an adequate margin, as defined by the performing physician (i.e. the ablation zone completely overlaps or encompasses the lesion plus an ablative margin), as assessed by CT, MRI, PET, US, and/or X-ray, immediately following the procedure.

2. Regional recurrence rate at a separate location in the liver (outside the initial treatment site(s)), evaluated at every visit after ablation of the target lesion(s), and overall evaluation at the 5-year follow-up, as assessed by CT, MRI, PET, US, and/or X-ray.

3. Recurrence-free survival, evaluated at every visit after ablation of the target lesion(s), and overall evaluation at the 5-year follow-up, as assessed by CT, MRI, PET, US, and/or X-ray.

4. Overall survival, evaluated at every visit after ablation of the target lesion(s), and overall evaluation at the 5-year follow-up.
5. Assess economic impact of ablation by capturing procedure-related items such as: complete procedure duration, ablation duration, number of ablations, length of hospital stay, and number and types of probes used.
6. Incidence of adverse events (AEs) (SAEs) that are deemed at least unlikely related to the procedure or device and all serious adverse events (SAEs) from the start of the ablation procedure through the end of the study.
7. Two QOL questionnaires: European Organization for Research and Treatment of Cancer (EORTC) QLQ-C30 and liver-specific QLQ-HCC18.

Note: These two questionnaires were chosen as tools to assess overall health status/quality of life in the patient population with soft-tissue liver lesions.
8. Numeric Pain Rating Score.

8.5 Analysis of Primary Endpoint

The number and percentage of patients and lesions achieving technical success will be summarized and a two-sided 95% confidence interval will be provided based on Clopper-Pearson's method. Technical success is achieved when the ablation is defined as a complete ablation by the performing physician. Technical success will be summarized at patient level and at lesion level. Technical success is achieved for a patient when all ablated lesions are defined as a complete ablation by the performing physician.

The number and percentage of patients and lesions achieving technique efficacy will be summarized and a two-sided 95% confidence interval will be provided based on Clopper-Pearson's method. Technique efficacy is achieved when the ablation is defined as a complete ablation by the performing physician. Technique efficacy will be summarized at patient level and at lesion level. Technique efficacy is achieved for a patient when all ablated lesions are defined as a complete ablation by the performing physician.

Target lesion recurrence will be summarized at patient level and at lesion level. Time-to-event analysis (survival analysis) using Kaplan-Meier's method will be utilized to estimate the target lesion recurrence rate at 3-month, 6-month, up to 60-month follow up. Cumulative incidence rate will be estimated for target lesion recurrence considering death as a competing risk and estimates will be presented at 3-month, 6-month, up to 60-month follow up. A two-sided 95% CI will be estimated for target lesion recurrence. Subjects who failed technique efficacy will be excluded from the analysis for target lesion recurrence.

First occurrence of a target lesion recurrence at patient level will be considered as the “event” for time-to-event analysis.

First occurrence of a target lesion recurrence at lesion level will be considered as the “event” for time-to-event analysis.

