17.9 Analyses to be Conducted

Categorical variables will be summarized descriptively by frequencies and associated percentages. Continuous variables will be summarized descriptively by number of patients, mean, standard deviation, median, minimum, and maximum. Confidence intervals will also be provided for procedure-related variables.

Disposition of Registry Patients

Patient disposition will be summarized using counts and percentages. The number and percentage of patients completed and discontinued along with the specific reasons for discontinuation will be tabulated.

Demographic and Baseline Characteristics

Summary statistics will be provided for patient demographics and pre-operative ablation characteristics.

Primary and Secondary Endpoint Analyses

Regression analysis methodologies will be utilized to explore the relationship between dichotomous clinical outcomes (technical success, technique efficacy, and secondary efficacy rate) and ablation procedure, patient, and provider parameters. Time to event analyses will be used for target lesion recurrence, regional recurrence rate, recurrence-free survival, progression free survival, and overall survival.

Complete details regarding all analysis methodologies including approaches to handle multiple lesions per patient, variable selection techniques, data reduction techniques given the number of potential independent variables, as well as subgroup analyses of interest will be specified in the SAP.

The number and percentage of patients achieving technical success will be summarized and a 95% confidence interval will be provided. A similar summary will be provided for technique efficacy, as well as for the primary and secondary efficacy rates, as previously defined.

Target lesion recurrence rates at each post-ablation scheduled visit will be estimated using the Kaplan-Meier method and 95% confidence intervals will be provided. A similar summary will be provided for the 5-year overall rate. Similar summaries will also be provided for regional recurrence rate, overall and progression-free survival rates for the entire observation period from the ablation procedure date through 5 years of follow-up.

Scores from the EORTC QOL questionnaires and Numeric Pain Rating Scales will be summarized with methodology consistent to the recommendations of the specific survey. Additional endpoints will be summarized with descriptive statistics.

Plans for Interim Analysis

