8.6 Analysis of Secondary Endpoints

The number and percentage of patients and lesions achieving secondary efficacy will be summarized and a two-sided 95% confidence interval will be provided based on Clopper-Pearson’s method. Analysis for secondary efficacy rate includes only repeat ablations for target and non-target lesions.

For patient level analysis – secondary efficacy is achieved for a patient when all re-ablations of target lesions and all re-ablations of non-target lesions are defined as a complete ablation by the performing physician. The denominator for subject level analysis will include subjects who had a re-ablation during visit 3 to visit 14 including unscheduled visits.

For lesion level analysis – secondary efficacy is achieved for a lesion when all repeat ablations of that lesion (target and non-target lesions) are defined as complete ablation by the performing physician. The denominator for lesion level analysis will include lesions that had a repeat ablation during visit 3 to visit 14 including unscheduled visits.

Regional recurrence rates will be estimated at patient level. Time-to-event analysis (survival analysis) using Kaplan-Meier’s method will be utilized to estimate the regional recurrence rate at 3-month, 6-month, up to 60-month follow up. Two-sided 95% CI will be estimated for regional recurrence rate. First occurrence of identification of a new lesion outside the initial treatment site(s) during visit 3 to visit 14 including unscheduled visits at patient level will be considered as the “event” for time-to-event analysis at patient level.

Recurrence-free survival rates will be estimated at patient level. Time-to-event analysis (survival analysis) using Kaplan-Meier’s method will be utilized to estimate the recurrence-free survival rate at 3-month, 6-month, and up to 60-month follow up. Two-sided 95% CI will be estimated for recurrence-free survival rate.

An “event” is defined for recurrence-free survival if any of the following conditions are met:

- a. First occurrence of a target lesion recurrence during visit 4 to visit 14 including unscheduled visits at patient level
- b. Identification of a new non-target lesion during visit 3 to visit 14 including unscheduled visits at patient level

c. Deaths from any cause of a patient during the follow up period

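### Lesion-level Clopper-Pearson intervals ignore that lesions are clustered within patients, so they overstate precision; patient-level intervals and point estimates are unaffected

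*SAP*

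**What the plan says.** SAP 8.5 reports the two binary primary endpoints in two units: "Technical success will be summarized at patient level and at lesion level", and likewise for technique efficacy. The interval is Clopper-Pearson in both units. For technical success, "patients and lesions achieving technical success will be summarized and a two-sided 95% confidence interval will be provided"; for technique efficacy, "The number and percentage of patients and lesions achieving technique efficacy will be summarized and a two-sided 95% confidence interval will be provided". SAP 8.6 extends the method to a secondary endpoint: "The number and percentage of patients and lesions achieving secondary efficacy will be summarized", again with Clopper-Pearson.

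The patient-level rule gives one result per patient: "Technical success is achieved for a patient when all ablated lesions are defined as a complete ablation by the performing physician". No such reduction applies at lesion level, where each lesion counts separately.

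Target lesion recurrence is also analysed in both units, by Kaplan-Meier and by cumulative incidence with death as a competing risk. At lesion level, "First occurrence of a target lesion recurrence at lesion level will be considered as the" event. On precision the SAP says only: "A two-sided 95% CI will be estimated for target lesion recurrence". It names no variance estimator.

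Protocol 17.9 lists what the SAP was to contain: "Complete details regarding all analysis methodologies including approaches to handle multiple lesions per patient". The SAP has no robust variance, GEE, mixed model, cluster bootstrap or design-effect correction. SAP 8.7 excludes sensitivity analyses. SAP 5 and 8.4 make all intervals descriptive, with no hypothesis tests.

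**The concern.** Protocol 8.0 admits patients with one or more lesions, and Protocol 12.1 defines target lesions as those ablated, or intended to be ablated, on the ablation day. A patient's target lesions therefore share a liver and an ablation day, and plausibly an operator and an imaging session. Positive correlation of their outcomes is the natural expectation. An exact binomial interval that counts every lesion as an independent trial then claims more information than the data hold.

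The registry tests no hypothesis, so the confidence interval is the main statement of uncertainty for these rates. An interval labelled 95% should have roughly that coverage. SAP 8.8 repeats the primary endpoints by disease type and by use of the confirmation software. If lesion counts differ between subgroups, the undercoverage will differ too.

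**Working it through.** **Inputs from the documents.** Clopper-Pearson, two-sided 95%, for lesions (SAP 8.5, 8.6). About 1,500 patients (the Protocol summary says up to 1,500; Protocol 7.2 says at least 1,500). One or more lesions per patient (Protocol 8.0).

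**Assumed inputs, because the documents give none.** Success 90% or 95%. Mean lesions per patient 1.3, 1.5 or 2.0, with counts following a Poisson distribution truncated at zero. Within-patient correlation ρ of 0.1, 0.3 or 0.5.

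**Formulas.** With m lesions per patient:

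- design effect = 1 + (E[m²]/E[m] − 1) × ρ
- required width multiplier = √(design effect)
- approximate coverage of the unadjusted interval = 2Φ(1.96/√(design effect)) − 1

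For a zero-truncated Poisson count, E[m²]/E[m] − 1 equals its parameter λ, where λ/(1 − e^(−λ)) is the mean. Means of 1.3, 1.5 and 2.0 give λ = 0.550, 0.874 and 1.594.

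**The plan's own figure.** The nominal 95% is reproduced only under independence. At ρ = 0, simulated coverage was 94.9% to 96.2% (4,000 registries per scenario, beta-binomial lesions within 1,500 patients).

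**One case in full.** Mean 2.0, ρ = 0.5: design effect = 1 + 1.594 × 0.5 = 1.797; √1.797 = 1.340. The 3,000 lesions carry the information of 3,000/1.797, or about 1,670 independent lesions. At 90% success the unadjusted half-width is 1.090 points, and the required one is 1.090 × 1.340 = 1.461. Approximate coverage is 2Φ(1.96/1.340) − 1 = 85.6%.

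**All cases** (half-widths in percentage points at 90% success; simulated coverage spans 90% and 95% success):

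| Mean lesions (total) | ρ | Design effect | Multiplier | Unadjusted → required half-width | Approx. coverage | Simulated coverage |
|---|---|---|---|---|---|---|
| 1.3 (1,950) | 0.1 | 1.055 | 1.027 | 1.357 → 1.394 | 94.4% | 95% |
| 1.3 | 0.3 | 1.165 | 1.079 | 1.357 → 1.465 | 93.1% | 94% |
| 1.3 | 0.5 | 1.275 | 1.129 | 1.357 → 1.532 | 91.7% | 92-93% |
| 1.5 (2,250) | 0.1 | 1.087 | 1.043 | 1.262 → 1.316 | 94.0% | 95% |
| 1.5 | 0.3 | 1.262 | 1.124 | 1.262 → 1.418 | 91.9% | 92-94% |
| 1.5 | 0.5 | 1.437 | 1.199 | 1.262 → 1.513 | 89.8% | 91% |
| 2.0 (3,000) | 0.1 | 1.159 | 1.077 | 1.090 → 1.174 | 93.1% | 92-93% |
| 2.0 | 0.3 | 1.478 | 1.216 | 1.090 → 1.325 | 89.3% | 90% |
| 2.0 | 0.5 | 1.797 | 1.340 | 1.090 → 1.461 | 85.6% | 86-87% |

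Simulated coverage tends to sit slightly above the approximation because Clopper-Pearson is itself conservative.

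**Dependence on the assumed spread.** A more skewed split with the same mean of 2.0 (45/28/14/8/5% with 1 to 5 lesions) gives E[m²] = 5.36. At ρ = 0.5 the design effect is 1 + (5.36/2 − 1) × 0.5 = 1.84, the multiplier is 1.356 and simulated coverage is 85-86%. The conclusion is not sensitive to the shape.

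**Dependence on registry size.** The design effect does not involve the number of patients, so enrolling more does not cure the problem. Simulations with 300 patients showed a similar pattern.

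No calculation was made for recurrence, because the SAP states no variance method to check.

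**The case against.** The strongest reply is that this matters little. The intervals are descriptive, there is no sample size calculation to upset, and every affected endpoint also has a patient-level result with a sound interval. Protocol 17.5 calls these patient-level outcomes, and Protocol 17.9 promises the technical success interval for patients; the lesion-level interval was added by the SAP. The rules that require all lesions to be complete, and that take the first recurrence per patient, are themselves ways of handling multiple lesions. With few multi-lesion patients and correlation near 0.1, coverage stays close to 95%. Even in the worst tabulated case the half-width grows by only 1.461 − 1.090 = 0.37 point.

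Most of this stands, and it limits the severity. It does not remove the defect. The patient-level rules settle only the patient-level analysis. Secondary efficacy is defined as a percentage of lesions (Protocol 6.3), so there the lesion-level figure is not an optional extra. At correlation 0.3 or more, the conservatism of Clopper-Pearson generally no longer hides the shortfall.

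A reader might infer three stronger things that the documents do not support:

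- That the intervals for all three primary endpoints are wrong as written. Patient-level intervals are not affected, and for recurrence no variance method is named.
- That the SAP prescribes ordinary Kaplan-Meier intervals for lesion-level recurrence. It does not say so; a standard Greenwood-type variance would share the fault, but that choice is still open.
- That one tumour type is hit hardest. The documents give no lesion counts by disease.

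**Conclusion.** The point holds for the lesion-level Clopper-Pearson intervals for technical success, technique efficacy and secondary efficacy. With positive within-patient correlation they are too narrow. Under the stated assumptions actual coverage is about 86-95%, and the intervals should be about 3-34% wider. At the low end the effect is negligible.

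The figures are for 1,500 patients. Secondary efficacy covers only re-ablated lesions, so its intervals will be wider in absolute terms, and its lesion counts per patient may differ from those assumed.

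For lesion-level target lesion recurrence, by Kaplan-Meier and by cumulative incidence, the finding is an unstated method. The protocol's commitment that the SAP would deal with multiple lesions per patient is met for the patient-level definitions but not for lesion-level precision.

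The consequence is overstated precision in descriptive results, not a biased estimate or a false test conclusion. This should be fixed before the final analysis; it does not threaten the registry's main results.

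**What to change.** - **Patient-level proportions:** keep Clopper-Pearson.
- **Lesion-level proportions:** keep the simple lesion proportion as the estimate and give a patient-clustered interval, either Clopper-Pearson on the effective sample size (lesions divided by the estimated design effect) or GEE with working independence and robust variance. Working independence matters because an exchangeable working correlation reweights lesions and can move the estimate.
- **Fallback:** where a subgroup has 0% or 100% success, the correlation cannot be estimated and the robust variance collapses. Name a substitute in advance, such as the patient-level exact interval.
- **Lesion-level recurrence:** for both the Kaplan-Meier and the cumulative incidence estimates, specify a patient-level cluster bootstrap or a robust variance.
- **Exploratory models (SAP 8.10):** state the unit of analysis. If the logistic and Cox models are fitted by lesion, use patient-clustered robust variance.

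The cost is a few sentences in the SAP and a little more programming, with no new data and no change in conduct. Lesion-level intervals become slightly wider. Because this changes methodology, it falls outside the minor modifications that SAP 8.1 allows without an amendment, and it is best settled before database lock.

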6.2 Primary Endpoints

The primary endpoints of this registry are below, based on different points in time:

Perioperative endpoint-

1. Technical success, defined as ablation of the target lesion(s) according to the protocol and covered completely, with an adequate margin, as defined by the performing physician (i.e. the ablation zone completely overlaps or encompasses the target lesion(s) plus an ablative margin), as assessed by CT, MRI, PET, US, and/or X-ray, immediately following the procedure.

Short term endpoint-

2. Technique efficacy, ablation of the target lesion(s) according to the protocol and covered completely, with an adequate margin, as defined by the performing physician (i.e., the ablation zone completely overlaps or encompasses the target lesion(s) plus an ablative margin), as assessed by CT, MRI, PET, US, and/or X-ray, at Visit 3 (between 7 days and less than 3 months post-ablation).

Long term endpoint-

3. Target lesion recurrence (local recurrence) rate evaluated at every visit after ablation of the target lesion(s), and overall evaluation at the 5-year follow-up, as assessed by CT, MRI, PET, US, and/or X-ray.

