7.7 Removal of Patients from the Registry

In accordance with the current revision of the Declaration of Helsinki and the Code of Federal Regulations, a patient has the right to withdraw from the registry at any time for any reason without prejudice to his/her future medical care by the physician or the institution. Should a patient (or patient's legally authorized guardian/representative) decide to withdraw from the registry, all efforts will be made to collect all AEs the patient may have experienced.

Participation may be terminated prior to completing the registry for any of the reasons listed below (reasons that do not fit the categories below will be documented as "other").

Withdrawal of Consent:

If a patient chooses to withdraw early from the registry, the patient should contact the site, which will then complete the Subject Completion/Discontinuation eCRF page. When a patient's participation is terminated prior to completing the registry, the reason for withdrawal is to be documented on the eCRF and in the source documentation.

Investigator Decision for Patient Termination:

The Investigator may withdraw a patient for any safety reason, including, but not limited to, the following reasons:

1. Inability of Investigator to locate and target the soft tissue liver lesion.
2. Inability of patient to tolerate the anesthesia.

Note: If a patient experiences an AE during probe puncture and is not ablated, this patient should be followed until AE resolution. If no AE occurred during probe puncture and the patient could not be ablated, the patient should be discontinued.

Death:

When available, the cause of death should be documented in the AE eCRF. The Subject Completion/Discontinuation eCRF also must be completed.

Lost to follow-up:

All patients should be encouraged to return for clinic visits for evaluation during the registry follow-up period. After all attempts to contact the patient have failed and after 2 consecutive missed visits to the site, a patient will be considered lost to follow up. Should the patient return to the site, their status in the database may be updated accordingly and data continue to be collected. For patients who are definitively lost to follow-up, the reason for early termination will be completed in the Subject Completion/Discontinuation eCRF.

Site Termination or Registry Termination:

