12.1 Visit 1 – Screening

The screening assessments for this visit may occur over several dates within 60 days prior to Visit 2. If the patient is not seen within a 60 day window of the Ablation Day (Visit 2), the Screening Visit may occur on the same day as the ablation procedure.

Patients will be selected for microwave ablation based on the pre-procedure investigations and the Investigator's opinion. Eligible patients will be provided with the registry information, including the ICF.

The following screening assessments will occur within 60 days prior to the ablation visit (Visit 2):

- Patients must be given ample time to review and sign the ICF, or have a waiver in place, where applicable.
- Collect demographic information (age at time of Visit 1, sex, race, ethnicity).
- Collect patient parameters, as outlined in Section 19.1, subsection 2.
- Perform a liver tissue assessment (if available): steatosis (mild, moderate, severe); fibrosis/cirrhosis (mild, moderate, severe; include pathology results and fibrosis stage, if known); liver stiffness (actual stiffness value in kilopascals, if known); vascular invasion (presence or absence); microsatellite instability (MSI; high [MSI-H], low [MSI-L], or microsatellite stable [MSS]).
- BCLC staging, if applicable

- Evaluate Eastern Cooperative Oncology Group classification (ECOG) performance status.
- Body Mass Index (BMI): height and weight.
- Child-Pugh Score, if applicable and American Society of Anesthesiologists (ASA) Score.
- SOC imaging used to determine the ablation plans (CT, MRI, PET, Ultrasound (US), and/or X-ray), even if not within the screening window, should be used to determine soft tissue liver lesion details (e.g., lesion size, lesion type, location, shape).
 - If a Screening Visit occurs and the patient's SOC scans do not fall within the screening window, then an additional scan is not required for the screening visit.
 - For purposes of this Registry, target lesions are defined as any lesions ablated or intended to be ablated on the Ablation Day (Visit 2). Non-target lesions are defined as any lesions not ablated or not intended to be ablated on the Ablation Day (Visit 2).
 - All SOC scans of the abdomen/liver (CT, MRI, and/or PET) should be submitted to the Sponsor.
- Laboratory tests if applicable, per site SOC; to be done within 60 days of the ablation procedure,
 - Coagulation tests, including, INR, PT and APTT (or PTT).

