1.2 Study Design

This is a multicenter, observational registry that follows patients for a total of up to 5 years from the date of the first liver ablation procedure with either the NEUWAVE Microwave Ablation System or the NEUWAVE Microwave Ablation System with Ablation Confirmation.

This is an “umbrella registry,” which was included as an optional component in other NEUWAVE studies; hence, data from consenting patients who are or will be enrolled in other NEUWAVE soft tissue liver lesion ablation studies will be included in this registry. All other patients will be enrolled and followed prospectively, enrolled retrospectively with prospective, longitudinal follow up, or enrolled retrospectively with all retrospective follow up.

2 Treatment Assignment

This is a single-arm registry where all enrolled patients will be ablated using the NEUWAVE Microwave Ablation System as part of the site’s SOC treatment or per protocol for those patients who are also enrolled in other NEUWAVE studies.

3 Randomization and Blinding Procedures

As this is a single-arm registry, no randomization will occur, and no blinding procedures are required.

4 Interval Windows

Interval windows are provided in the Schedule of Assessments section of the study protocol. No additional windows are planned for analysis purposes.

5 Levels of Significance

No levels of significance are specified as no specific hypotheses about any of the outcomes of interest are being formulated or tested. Two-sided 95% confidence intervals (CI) will be estimated for specific endpoints for descriptive purposes only.

6 Analysis Sets

All Enrolled Set (AES): Consists of subjects who signed informed consent form or retrospectively enrolled with a waiver for signing informed consent form. The AES will be used for disposition of study subjects.

Full Analysis Set (FAS): FAS Consists of subjects who met inclusion/exclusion criteria and to whom the NeuWave Ablation device was utilized during procedure. Primary and secondary endpoints will be analyzed using FAS.

Safety Analysis Set (SAF): SAF Consists of subjects who met inclusion/exclusion criteria and to whom the NeuWave Ablation device was utilized during procedure. Safety endpoints will be analyzed using SAF.

7 Sample Size Justification

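### SAP 8.5 judges technical success and technique efficacy on ablated lesions only, so a patient with a planned but unablated target lesion is scored a success

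*SAP*

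**What the plan says.** Protocol 6.2 gives the perioperative endpoint as "Technical success, defined as ablation of the target lesion(s) according to the protocol and covered completely, with an adequate margin". SAP 8.4.1 repeats that definition, and both documents define technique efficacy at Visit 3 in the same terms. The unit is the target lesion. Protocol 12.1 says which lesions those are: "target lesions are defined as any lesions ablated or intended to be ablated on the Ablation Day (Visit 2".

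SAP 8.5 then sets the scoring rules, and these use a different unit. For technical success at patient level: "Technical success is achieved for a patient when all ablated lesions are defined as a complete ablation by the performing physician". For technique efficacy: "Technique efficacy is achieved for a patient when all ablated lesions are defined as a complete ablation by the performing physician". The general rule, which is all that the lesion-level summary has to go on, reads: "Technical success is achieved when the ablation is defined as a complete ablation by the performing physician". SAP 8.5 states no lesion-level denominator for either endpoint. SAP 8.6 does state one for secondary efficacy: "The denominator for lesion level analysis will include lesions that had a repeat ablation during visit 3 to visit 14".

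The primary endpoints are analysed in the full analysis set (SAP section 6): "FAS Consists of subjects who met inclusion/exclusion criteria and to whom the NeuWave Ablation device was utilized during procedure". Protocol 7.6 records patients whose ablation was never initiated as screen failures. SAP 8.5 excludes from the target lesion recurrence analysis only subjects who failed technique efficacy. SAP 8.7 plans no sensitivity analysis.

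**The concern.** A target lesion that was planned for treatment and not ablated cannot meet a definition that requires the lesion to be ablated and fully covered. The SAP 8.5 rule never looks at that lesion. SAP 8.5 therefore departs from SAP 8.4.1 as well as from the protocol, and a programmer following it will report something other than the defined endpoint.

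Three things follow:

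- Two of the three primary endpoints can be overstated, always in the favourable direction.
- The third is touched as well. A patient wrongly scored as a technique efficacy success enters the recurrence analysis with a target lesion that was never treated.
- Nothing in the plan would show the difference, because no alternative scoring is specified.

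**Working it through.** The documents state no expected success rate, no frequency of untreated target lesions and no sample size calculation, so there is no figure of the plan's own to reproduce. The check has two parts.

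**1. The rules applied to one patient.** Take a patient with three target lesions, two completely ablated and one that could not be reached.

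| | Defined endpoint (protocol 6.2 and 12.1, SAP 8.4.1) | SAP 8.5 rule |
|---|---|---|
| Patient level | Failure: one target lesion not ablated | Success: both ablated lesions complete |
| Patient in denominator? | Yes, device used | Yes, device used |
| Lesion level | 2 of 3 | 2 of 2, by implication only |
| Recurrence analysis | Excluded as a technique efficacy failure | Retained |

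At patient level the denominator is the same under both rules and the numerator is wrong. At lesion level the numerator is the same and the denominator shrinks, if untreated lesions are indeed left out.

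**2. Direction and size.** Every patient with all target lesions complete also has all ablated lesions complete, so the patient-level SAP rate cannot be below the defined rate. At lesion level the same count of successes is divided by an equal or smaller number.

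Let s be the success proportion under the SAP rule and u the share of units affected. At patient level u is the share of patients with at least one target lesion ablated and at least one not; at lesion level it is the share of target lesions not ablated. Taking s to be the same in affected and unaffected patients, the defined rate is s(1 − u) and the overstatement is s − s(1 − u) = s·u.

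Both s and u are assumptions. The n of 1500 is the enrolment figure in the protocol summary, used for illustration; the number of lesions is not given. Half-widths are from Clopper-Pearson intervals, the SAP's method.

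| s | u = 0.5% | u = 1% | u = 2% | u = 5% | Half-width at n = 1500 |
|---|---|---|---|---|---|
| 90% | 0.45 | 0.90 | 1.80 | 4.50 | (91.47 − 88.37)/2 = 1.55 |
| 95% | 0.48 | 0.95 | 1.90 | 4.75 | (96.05 − 93.77)/2 = 1.14 |
| 98% | 0.49 | 0.98 | 1.96 | 4.90 | (98.65 − 97.16)/2 = 0.75 |

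Entries are percentage points. In counts, with s = 95% and u = 2%:

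- Patient level: SAP rule 1425/1500 = 95.0% (93.8 to 96.1); defined endpoint 1396/1500 = 93.1% (91.7 to 94.3).
- Lesion level, 1500 target lesions: SAP rule 1396/1470 = 95.0% (93.7 to 96.0); defined endpoint 1396/1500 = 93.1% (91.7 to 94.3).

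The overstatement passes the half-width when u exceeds half-width/s: 1.55/0.90 = 1.7%, 1.14/0.95 = 1.2%, and 0.75/0.98 = 0.8%.

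**The case against.** Several objections have force.

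- **A reader might infer that failures leave the denominator.** For the patient-level rule they do not: the partly treated patient stays in and is misclassified. At lesion level the loss is implied, not stated. The table shells are a separate document (SAP section 10) and may settle it.
- **A reader might infer that this rule removes patients in whom nothing could be ablated.** Protocol 7.7 lists "Inability of Investigator to locate and target the soft tissue liver lesion" as a ground for withdrawal. It shows that failure to treat is foreseen, but patients with no ablation leave through protocol 7.6 and the full analysis set definition. Rewording SAP 8.5 would not bring them back.
- **A reader might infer a proven inflation of 2 to 5 points, larger than the sampling error.** The documents support no particular frequency. At 0.5% the effect is inside the half-width at every success rate tabulated.
- **A reader might infer that models of success by lesion location are biased.** That is plausible, because hard-to-reach lesions may cluster by position, but it is not shown. Protocol 7.7 also lists intolerance of anesthesia, which has nothing to do with location. Location is not a SAP 8.8 subgroup, and it could enter SAP 8.10 only as one unnamed patient parameter.
- **The protocol's wording is not perfectly clean.** The companion definition of non-target lesions in 12.1, read literally, also catches a lesion that was planned but not ablated. This overlap is a reason to state the class of such lesions. It does not support ablated-only scoring, because the target definition expressly makes intent sufficient.
- **Nothing is tested.** Protocol 17.5 and SAP section 5 set no hypotheses, and the intervals are descriptive. This limits the severity. It does not excuse one SAP from carrying two incompatible rules for a primary endpoint.

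**Conclusion.** The point holds as a conflict between the SAP's scoring rule and its own endpoint definition. A patient with a planned but untreated target lesion is counted as a success on technical success and technique efficacy, and is retained for recurrence. The reported rates can only equal or exceed the defined ones. By assumption, the excess runs from about 0.5 points with 0.5% of units affected to 4.5–4.9 points with 5% affected, for success of 90–98% among ablated lesions. If such lesions are very rare, little changes. The conflict between the passages is certain; the size is unknown. Because the estimates are descriptive and the models exploratory, this should be fixed but does not undermine the registry.

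**What to change.** In SAP 8.5, for both endpoints:

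- Require completeness of every target lesion as protocol 12.1 defines it, including those planned for Visit 2 and not ablated, in place of ablated lesions only. Say that such a lesion is classed as target.
- Count it as a failure at lesion level, and count the patient as a failure at patient level.
- State both denominators, as SAP 8.6 does for secondary efficacy.
- Report the ablated-only rate as supportive.

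Report separately, as a count, the patients with no lesion ablated, who stay outside the full analysis set. State whether a patient who was punctured but not ablated (protocol 7.7) counts as having had the device used.

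The cost is mainly wording, and success rates that may be slightly lower. There is one check to make first. Protocol 19.1 lists no explicit field for lesions planned but not ablated, so the sponsor must confirm that the eCRF records them. For fully retrospective patients (protocol 9.3) intent may not be recoverable from the chart. If so, report how many patients lack the information, and give the rates for prospectively enrolled patients alongside.
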